### **Patient Health and Experience Outcomes:**

Self-Reported Disability (Primary Outcome): using the RMDQ, which demonstrates reliability, validity, and responsiveness in people with acute and chronic LBP.

Pain Intensity: using a Numeric Pain Rating Scale (0-10) for pain at rest, pain when walking, and pain when lifting a bag of groceries from the floor. Each will be reported on a scale of 0 (no pain at all) to 10 (worst imaginable pain).

Health-Related Quality of Life: using the EuroQOL-5D (EQ-5D-5L), which demonstrates good reliability and validity, and is suitable for economic evaluation in LBP. The EQ-5D-5L VAS score (0-100) will be reported as a patient health outcome. The EQ5D responses will be converted to an EQ5D index value using the value set calculated for the Canadian context. The index value will be reported as a patient-level health outcome and will also be used to calculate quality-adjusted life years (QALY) for our outcome in the economic evaluation.

Global Rating of Change: using an 11-point global rating of change scale, from a great deal better (+5) to a great deal worse (-5), as has been recommended for self-reported rating of change.

Participant satisfaction: using an 11-point scale for satisfaction with care, extremely dissatisfied (-5) to extremely satisfied (+5).

Adverse events: using an adverse events questionnaire consistent with reporting guidelines that asks: 1) if the patient participant has experienced any adverse event(s) as a result of any of the treatments received; 2) what adverse event(s) were experienced; 3) how long the event(s) lasted; and 4) how severe each adverse event was. For analysis, adverse events will be identified as serious or non-serious. An adverse event will be identified as serious if any of the following criteria are met: the participant requires in-patient hospitalization or an emergency department visit due to the adverse event,

the adverse event results in significant and persistent disability (beyond 72 hours), or the adverse event is life-threatening or results in death. These responses are being monitored as they are completed in order to provide ongoing oversight of patient participant safety.

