The following measures will be assessed as secondary outcomes, reported in the trial results, and included in the process evaluation as potential mechanisms through which the PT-led primary care model influences LBP-related disability.

**Self-efficacy:** confidence in abilities to participate in usual activities using the Pain Self-Efficacy Questionnaire (PSEQ)

**Psychosocial risk factors for persistent pain and disability:** The Pain Catastrophizing Scale (PCS), Tampa Scale of Kinesiophobia 11 (TSK-11), and 2-item Patient Health Questionnaire (PHQ-2) will measure psychosocial factors associated with pain-related disability.

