Pain intensity, health-related quality of life (EQ-5D-5L), PSEQ, PCS, TSK-11, and PHQ-2 outcomes will be analyzed as described for the primary outcome, adjusted for the same covariates. Patient satisfaction and global rating of change outcomes have no baseline measures, and will be analyzed using ordinal logistic regression with clusters as random effects, adjusting for the same covariates as described above. When individual items are missing from within any of the questionnaires, we will use simple mean imputation as suggested by Chavance. Serious adverse events will be presented descriptively by arm due to low expected counts. Any adverse events (yes/no) will be presented as incidence rates with confidence intervals and compared by calculating relative risks with confidence intervals from robust Poisson regression using GEE-type robust variance estimators (using *PROC GLIMMIX* with *EMPIRICAL* option in SAS) to account for clustering and using an exchangeable working correlation matrix. We will use empirical covariance (“sandwich”) bias-adjusted (residual-based) estimators and the Fay and Graubard correction to account for small number of clusters in all models comparing incidence rates. In the case of non-convergence or unstable estimates due to the small number of clusters, we would attempt to fit the model using an independent working correlation matrix. Other information related to non-serious adverse events (i.e., severity and duration) will be reported descriptively.

We have planned a secondary analysis, a responder analysis, to compare the proportion of participants who experience a meaningful improvement in disability (RMDQ) in the PT-led primary care model arm versus the usual care arm. We will define a meaningful improvement as an improvement of greater than or equal to 30% improvement on the RMDQ, corresponding to an established minimally important difference among people with LBP. We will calculate the proportion of participants who

experience a meaningful improvement in each arm and compare between groups using robust Poisson regression, with GEE-type robust variance estimators to account for clustering. We will use empirical covariance (“sandwich”) bias-adjusted (residual-based) estimators and the Fay and Graubard correction to account for small number of clusters.

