#### Economic evaluation

We will estimate the cost-effectiveness of the PT-led care model from both a societal (primary) and health system payer (secondary) perspective to meet the needs of all knowledge users. The total costs will be determined by multiplying the quantity of resource use (or lost days) by the corresponding unit cost (or hourly wage), summing the total cost over each follow-up interval, and then calculating the mean cost at each follow-up time point, as well as an overall mean cost for the entire one-year study period. Results will be presented as aggregated and disaggregated costs. Utility data will be generated using EQ-5D-5L index values (ie. utility scores) from all follow-up assessment time points. We will estimate QALYs for every participant, using the area under the curve approach, assuming linear interpolation between the measurements. To accommodate the hierarchical structure of the data, we will use bivariate multilevel modeling to estimate the incremental cost-effectiveness ratio using a calculation of cost-per-QALY gained for PT-led primary care versus usual care and to estimate the incremental net benefit at various willingness to pay values. To account for clustering of study sites, as well as heterogeneity in costs and treatment effect across jurisdictions, we will model treatment group as

a fixed effect and the study site a random effect; adjusting for the same covariates as the primary analyses as fixed effects in our models. We will conduct a probabilistic sensitivity analysis using 10,000 Monte Carlo simulations to present the uncertainty in our cost-effectiveness estimates. Simulation results will be plotted on cost-effectiveness planes and we will generate cost-effectiveness acceptability curves to display the probability that the PT-led care model is cost-effective across a range of willingness to pay thresholds.

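### Simple mean imputation of missing items is applied to every questionnaire, including the EQ-5D-5L, where it usually gives a level that the value set cannot score

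*Combined protocol and SAP*

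**What the plan says.** The item-level rule is one sentence in the Analysis section, under Patient health and experience outcomes: "When individual items are missing from within any of the questionnaires, we will use simple mean imputation". It refers for the method to a cited paper on missing items in quality-of-life studies. The plan itself does not say whether the mean is over the participant's own answered items or over the sample for that item. It gives no rounding rule and no minimum number of answered items, and it exempts no instrument.

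The EQ-5D-5L is among the outcomes listed in the same paragraph: "Pain intensity, health-related quality of life (EQ-5D-5L), PSEQ, PCS, TSK-11, and PHQ-2 outcomes will be analyzed as described for the primary outcome". Under Patient Health and Experience Outcomes in the Methods: "The EQ5D responses will be converted to an EQ5D index value using the value set calculated for the Canadian context". The index is a patient-level outcome and "will also be used to calculate quality-adjusted life years (QALY) for our outcome in the economic evaluation". Under Economic evaluation: "Utility data will be generated using EQ-5D-5L index values", with a QALY for every participant by area under the curve. That section has no rule for a missing utility.

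For scores missing at a visit, the plan relies on REML under MAR. The imputation-based MNAR sensitivity analysis covers missing RMDQ values only.

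**The concern.** Averaging items makes some sense where the items of a scale measure one thing and are summed. The EQ-5D-5L is not built that way. Its dimensions are different attributes, and the index depends on which level was chosen on which dimension. A fractional level is not a state that respondents can report. The analyst would have to round it, drop it or extend the scoring in some other way, and would choose after the data are in, although the document's stated purpose is to fix analytic decisions beforehand. Where the mean happens to be whole, the rule still assigns a level on one attribute from answers about others.

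At stake are the EQ-5D index as a reported outcome and the QALYs in the cost-utility analysis.

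A secondary, conditional issue concerns the summed scales. If the mean is over the participant's own items, a few answers can set a complete score. That score then counts as observed and bypasses the plan's handling of missing scores.

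**Working it through.** **Plan's own figure.** The documents give no rate of item-level missingness and no figure for this rule, so there is nothing to reproduce on the point itself. The sample-size inputs are used only in step 4.

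**1. EQ-5D-5L, mean of the participant's own answered dimensions.** Assumption: five dimensions, each with levels 1 to 5, and a value set defined on whole levels. The documents do not print the value set. If k dimensions are answered, the imputed level is whole only when their sum is divisible by k. Counting all patterns equally:

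- k = 4: 5^4 = 625 patterns, of which 157 have a sum divisible by 4. Not whole: 625 − 157 = 468, or 74.9%.
- k = 3: 84 of 125, or 67.2%.
- k = 2: 12 of 25, or 48%.
- k = 1: always whole, but one answer is copied to every dimension.

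With an assumed skewed distribution over levels 1 to 5 (0.35, 0.30, 0.22, 0.10, 0.03), the shares are 75.2%, 66.6% and 48%, so equal weighting does not drive the result. For example, answers 1, 1, 2, 3 give 7/4 = 1.75, which is not a level. Answers 1, 2, 2, 3 give 2, which can be scored but says nothing specific about the missing attribute.

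**2. EQ-5D-5L, sample item mean.** The average of a dimension over many participants is almost never whole. Rounding would give everyone who skipped that dimension the same level.

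**3. Summed scales, only if the mean is over the participant's own items.**

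- PHQ-2 (two items): one answer is doubled.
- RMDQ: assume 24 yes/no items (the documents give no item count), independent items and 50% endorsement. With m items answered, the error SD of the prorated score is 24 × √[(0.25/m)(1 − m/24)].
  - m = 3: 24 × √(0.08333 × 0.875) = 6.5 points.
  - m = 20: 24 × √(0.0125 × 0.16667) = 1.1 points.
- For comparison, Sample Size and Power Calculations uses an SD of 5.7 and a target difference of 2.5.

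Under a sample item mean the failure is different. Take a participant whose true score is 20 of 24 and who answers 2 items, with an assumed item mean of 0.4. The score is 2 × 20/24 + 22 × 0.4 = 10.5, so the sample average largely sets it.

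**4. Size for the primary result.** From the plan: 63 patients per cluster, 9 clusters per arm, ICC 0.1, cluster autocorrelation 0.5, individual autocorrelation 0.6.

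- 1 + 62 × 0.1 = 7.2.
- r = (63 × 0.1 × 0.5 + 0.9 × 0.6)/7.2 = 0.5125.
- Design effect = 7.2 × (1 − 0.5125²) = 5.31.
- SE = 5.7 × √(2 × 5.31/567) = 0.78. Normal-approximation power is 89.3%, which agrees with the stated 90%.

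Now assume, as a bad case, that 5% of 12-month forms have only 3 of 24 items answered, with items missing at random. The added variance is 0.05 × 6.5² ≈ 2.1, against 5.7² = 32.5. Relative to the clustered variance this is 2.1/(32.5 × 5.31) ≈ 1.2%, so the SE rises by about 0.6% (noise at follow-up only).

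**The case against.** Five arguments can be made for the plan.

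- **The method is delegated to a cited paper.** That paper may specify the type of mean and a minimum number of answers. This stands. A reader might infer that there is no floor at all, but the documents support only that none is restated in the plan. The citation does not settle the EQ-5D-5L, because the plan's own sentence extends the rule to any questionnaire.
- **The wording suggests isolated skips.** It speaks of individual items missing from within a questionnaire, and Data Collection and Management describes frequent reminders and completion in person or by phone. This stands for the RMDQ: nothing shows that nearly empty forms occur or would be scored. It does not help the EQ-5D-5L, where one skipped dimension is enough.
- **A state that cannot be scored is a visible failure.** No invalid index arises until someone adds a step. That is fair, but the missing step is the gap: it would be chosen after the data are seen.
- **The 75% is a share of answer patterns.** It applies to forms that already lack exactly one dimension, and it is not an effect on the index, the QALYs or the trial. This also stands.
- **The primary result is hardly affected.** A reader might go from the 6.5-point error to a compromised primary outcome. The documents do not support that. The figure needs a person mean, an assumed item count, 50% endorsement (where the variance is largest) and forms with three answers. Even the assumed 5% case moves the SE by well under 1%, and items missing at random under a person mean add noise, not bias.

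**Conclusion.** The concern holds for the EQ-5D-5L. The stated rule covers the instrument, and neither reading of the mean suits it: most person means and almost all sample means are not valid levels, and the remainder have no sound meaning. The result rests on discrete levels and on a value set defined on them. The affected results are the index outcome and the QALYs. How much they would change cannot be stated, because the item-missing rate is not given.

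For the PHQ-2 and RMDQ, the concern is conditional on a person mean and, for the RMDQ, on nearly empty forms. Here the plan needs clarification; the documents do not establish an error. The effect on the primary comparison is likely small, and no sample-size or power figure changes. The EQ-5D-5L rule should be changed before analysis begins.

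**What to change.** **EQ-5D-5L.** Exclude it from item-level mean imputation. If any dimension is missing at a visit, set the index to missing at that visit. Analyse the index in the planned mixed model under MAR. Before computing QALYs, multiply impute missing index values with arm, site and the primary-model covariates in the imputation model. This last step is needed because Economic evaluation has no rule for a missing utility and the planned imputation covers only the RMDQ.

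**Other multi-item scales.** State that the mean is over the participant's own items and set a minimum share answered. A threshold of 80% is one reasonable choice, not one taken from the documents; on the 24-item assumption, 20 of 24 answered (83%) keeps the error near 1.1 points. Below the minimum, treat the score as missing under MAR. With two items, a half-answered PHQ-2 would then be missing. Report item missingness by arm.

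**Cost.** A few sentences in the plan, slightly more scores classed as missing, and a small amount of imputation work for the QALYs. No new data are needed. Analysis is due to start only after data collection ends, and the document already provides for amendments through the trial registry.

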#### Healthcare utilization and missed occupational activity outcomes

For healthcare utilization and missed occupational activities outcomes, we will estimate the average effect at the patient level across the population (marginal models), accounting for clustering using GEE-type robust variance estimators and robust Poisson regression with an exchangeable working correlation matrix. All of the models generated for our healthcare utilization and missed occupational activities outcomes will include the same covariates as our analysis for patient health outcomes: age, sex, highest level of education achieved, income, duration of current episode of LBP, and Functional Comorbidity Index score (individual level), and primary care site rurality and number of active patients (cluster level). In the case of non-convergence or model instability, a possibility for any binary outcomes with very low or high event rates given our small number of clusters, we will attempt to model outcomes using an independence working correlation matrix. If we continue to experience issues with non-convergence or instability with alternate covariance structures, we will remove covariates, starting with duration of pain and income based on theoretical grounds and existing evidence on the strength of relationships between our covariates and our outcomes.

Primary care physician or nurse practitioner visits will be presented as rates and compared using rate ratios with adjusted Poisson or negative binomial regression. Other healthcare utilization within the primary care team (whether there were any other consultations with interprofessional team members and whether or not there was group programming accessed), and healthcare utilization outside of the primary care team (medications, diagnostic imaging, walk-in clinic visits, ED visits, specialist physician visits, emergency department visits, hospital admissions, interventional procedures, surgeries, other health provider visits) will be presented as incidence rates and compared by calculating relative risks with confidence intervals using robust Poisson regression, accounting for clustering. These models will use time as an offset to account for variable follow-up times and will incorporate empirical covariance (“sandwich”) bias-adjusted (residual-based) estimators and the Fay and Graubard correction to account for small number of clusters. Time (days) lost from occupational activities (paid employment, volunteer, homemaking, or educational activities) and assistance required (hours of paid assistance, hours of unpaid assistance) due to LBP will be presented as rates and compared using rate ratios with negative binomial regression.

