### **Sample Size and Power Calculations:**

We used the methodology of Teerenstra et al. to calculate the required number of clusters based on an ANCOVA analysis for the primary outcome (Roland-Morris Disability Questionnaire [RMDQ]) at 12 months adjusting for baseline. Our target sample was 20 clusters (10 per arm) allowing for 1560 patient participants (78 per practice before attrition). Conservatively accounting for attrition of two clusters (resulting in 18 clusters) and 20% of patients (resulting in 63 patients/cluster), this target would achieve 90% power to detect a minimally important mean difference of 2.5 points (Cohen's  $d=0.4$ ) using a two-sided  $\alpha=0.05$  and assuming a standard deviation (SD) of 5.7 points based on pilot study data, a conservative intracluster correlation coefficient of 0.1, a cluster autocorrelation coefficient (correlation between cluster means at baseline and follow-up) of 0.5, and an individual autocorrelation coefficient (correlation between participant scores at baseline and follow-up) of 0.6 informed by our pilot study. An average rate of 1.5 patient participants per site each week over one year would achieve the recruitment target of 1560 participants, which we anticipated based on our pilot study where we recruited and retained four sites and achieved a recruitment rate of >1.7 participants/site/week. Recruitment of 400 patient participants across 18 clusters (22 participants/cluster) would achieve 80% power.

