### **Participant Characteristics:**

The following characteristics and demographic information were collected from patients at baseline: age, first three digits of their postal code (to determine rural/urban status), biological sex, gender, identification as a member of a racialized group, duration of the current episode of LBP, previous history of LBP, number of other pain locations, highest level of education achieved, household income, and work status. In addition, the following questionnaires were administered at baseline as potential covariates and to inform subgroup analyses as part of our process evaluation.

Functional Comorbidity Index: an 18-item list of comorbidities that are associated with physical functioning. Each comorbidity is assigned a score of 1 and the total score is the sum of the comorbidity elements.

Keele STarT Back Tool: categorizes patients with LBP into low, medium, or high risk of persistent pain and disability based on physical and psychosocial risk factors.

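### The utilization, missed-activity, satisfaction and change-rating models leave out baseline back-pain severity, and the missed-activity model leaves out work status, although both were collected

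*Combined protocol and SAP*

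**What the plan says.** Under Patient health and experience outcomes, the primary RMDQ model has eight covariates: site rurality and practice size, and six patient characteristics. Baseline RMDQ is not listed because it enters as the first repeated measurement, with the arm difference at that time constrained to zero. Pain intensity, EQ-5D-5L and the psychosocial scales follow the same model.

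The same section notes that "Patient satisfaction and global rating of change outcomes have no baseline measures". It gives these two outcomes ordinal logistic regression with random site effects and the primary model's covariates. Nothing replaces the missing baseline.

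Under Healthcare utilization and missed occupational activity outcomes, every model takes "age, sex, highest level of education achieved, income, duration of current episode of LBP, and Functional Comorbidity Index score" at the individual level and the two site factors. If a model stays unstable after the working correlation is changed, covariates are removed, beginning with episode duration and income. One outcome is "Time (days) lost from occupational activities (paid employment, volunteer, homemaking, or educational activities", compared by a negative binomial rate ratio.

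Table 1 schedules RMDQ and pain intensity at baseline. Participant Characteristics lists "highest level of education achieved, household income, and work status" among the items collected. Of the Functional Comorbidity Index and the STarT Back tool, it says that "the following questionnaires were administered at baseline as potential covariates" and for subgroup analyses. Only the comorbidity index enters the models. STarT Back reappears in the Process evaluation analysis as an exploratory subgroup factor, which is not covariate adjustment.

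**The concern.** Reusing the primary model's covariate list looks like equal treatment, but it is not. The primary model deals with baseline severity outside the list. An outcome with no baseline value of its own receives the list and loses the severity adjustment. The only back-pain-specific item left is episode duration, which is among the first to be removed.

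The plan itself treats the omitted variables as prognostic. The intervention description ties recommended care to STarT Back risk, and the process evaluation states utilization and cost hypotheses by risk group. Days lost from paid work can arise only in people who work.

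Research question 2 (physician workload, utilization, missed work) rests largely on these models. Randomization was stratified by region and constrained on practice size and rurality, not on patient severity or employment. Sites were randomized in July 2023 and patients recruited from October 2023. The bias-protection section acknowledges identification and recruitment bias in that situation.

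**Working it through.** **Inputs from the plan.** The sample-size section states that "this target would achieve 90% power to detect a minimally important mean difference of 2.5 points", "assuming a standard deviation (SD) of 5.7 points based on pilot study data" and "a conservative intracluster correlation coefficient of 0.1". It also gives cluster and individual autocorrelations of 0.5 and 0.6, 20 sites (10 per arm), 78 patients per site, and 63 after attrition.

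**The plan's own figure.** With 9 sites of 63 per arm:
- D = 1 + 62 × 0.1 = 7.2
- r = (6.3/7.2) × 0.5 + (0.9/7.2) × 0.6 = 0.5125
- design effect = 7.2 × (1 − 0.5125²) = 5.309
- SE = 5.7 × √(2 × 5.309/567) = 0.780
- power = 89.3% by normal approximation, against 90% stated

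The figure reproduces. It concerns RMDQ only; the plan gives no power for the outcomes discussed here.

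**Chance imbalance in severity.** SE of the arm difference in mean baseline RMDQ = 5.7 × √[(2/10) × (ICC + (1 − ICC)/63)].
- ICC 0.1: 5.7 × √(0.2 × 0.1143) = 0.86 points
- ICC 0.02 (assumed): 5.7 × √(0.2 × 0.0356) = 0.48 points

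With 78 per site and ICC 0.1 it is 0.85, a 95% range of ±1.67 points.

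**What chance imbalance does to inference.** Two sets of simulations, 400 runs per scenario, used gradients that the documents do not give.
- Poisson regression with cluster-robust variance and the Fay-Graubard correction, independence working correlation, visit rate 1.2- or 1.5-fold per SD of RMDQ, ICC 0.02 or 0.1. With chance imbalance only, type I error without severity adjustment was 4.5-6.0%. Adjustment lowered the empirical SE by about 1-14%.
- Overdispersed Poisson outcomes, 20 sites of 63, 1.16- to 1.57-fold per SD, residual site SD 0.15-0.35 on the log rate. Adjustment lowered the SD of the log rate ratio by 1-21%. The mid-value was 7.5%, or 1/0.925² = 1.17 times the information.

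**Differential recruitment.** A systematic 1-point shift is 1/5.7 = 0.175 SD. Bias factor = (ratio per SD)^0.175:

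| Assumed ratio per SD | Bias factor |
|---|---|
| 1.2 | 1.03 |
| 1.5 | 1.07 |
| 2.0 | 1.13 |

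In the first simulation set (1.2 and 1.5), such a shift biased the unadjusted log ratio by +0.035 to +0.081. Adjustment for RMDQ brought it to about zero. These figures take no credit for absorption by the listed covariates.

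**Work status.** Assume 60% employed and ICC 0.02-0.1. SE of the arm difference in proportion employed = √[0.2 × 0.24 × (ICC + (1 − ICC)/63)] = 0.041 to 0.074. Split an imbalance d evenly around 0.6. If workers lose m times as many days as others, the spurious ratio is [1 + (m − 1)(0.6 + d/2)] / [1 + (m − 1)(0.6 − d/2)].
- m = 1.5: 1.016 to 1.029
- m = 3: 1.038 to 1.070
- paid-work days alone, non-workers contributing zero: (0.6 + d/2)/(0.6 − d/2) = 1.07 to 1.13

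**Measures affected.** Rate ratios (physician or nurse practitioner visits, days lost, hours of assistance), relative risks (other utilization) and odds ratios (satisfaction, global rating). No magnitude was computed for the ordinal models.

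**The case against.** The strongest reply is that the planned analysis is already valid under randomization. A reader might infer that any imbalance between sites feeds directly into the estimates and is credited to the care model. The documents do not support that. For chance imbalance, the utilization models specify cluster-robust variance with a small-sample correction, and the ordinal models carry a random site effect. The simulated type I error near 5% agrees for the Poisson case. Nor would an imbalance go through whole: age, income, education, episode duration and comorbidity absorb whatever part they share with severity or employment. This reply stands, and it leaves chance imbalance as a loss of precision.

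On recruitment, the plan is not passive. It used consecutive invitation, the same information in both arms, allocation withheld until after consent and baseline data collection, and research assistants who did not know the patients. These steps lower the risk but do not remove it, since staff at unblinded sites identified the candidates.

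A reader might also take 7-13% as the size of the work-status problem. That needs a separate model of paid-work days. The plan defines days lost across paid, volunteer, homemaking and educational activities, so people without paid work can contribute.

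Finally, STarT Back was collected only as a potential covariate, which is no commitment, and eight covariates on 20 sites already strain models for rare outcomes. That argues against making new terms impossible to remove. It does not argue against including them where the model fits.

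**Conclusion.** The gap is real. No model for these outcomes adjusts for baseline severity, the missed-activity model does not adjust for work status, and no other section restores either. It deserves correction before analysis, but it does not touch the primary outcome and does not invalidate the planned intervals under chance imbalance.

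Two consequences should be kept apart. Chance imbalance costs precision, roughly 1-20% of the standard error. Differential recruitment would be a bias outside the intervals, about 3-13% per RMDQ point. Both ranges depend on severity gradients that are assumptions. The documents do not show that a recruitment shift occurred. For work status, about 2-7% on the combined days-lost rate ratio is the relevant range for a one-SE imbalance, given the assumed employment rate, ICC and 1.5- to 3-fold difference in days lost.

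**What to change.** Before analysis begins, amend the plan by the registry route that it describes:

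- Add baseline RMDQ, or STarT Back risk group, to all utilization and missed-activity models and to the satisfaction and global-rating models. Name one of the two in advance.
- Add baseline work status to the missed-occupational-activity model.
- Place these terms late in the covariate-removal order, after duration and income, and still allow their removal for rare binary outcomes that do not converge.

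The data exist, and withholding allocation until baseline collection was complete supports using them as covariates. The cost is wording, one or two model degrees of freedom, and a slightly higher chance of non-convergence for rare outcomes. Adjustment will remove only the part of any recruitment difference that the chosen measure captures. Adding the terms after results are seen would be a discretionary choice of the kind this plan was published to prevent.
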